5 ANALYSIS SETS

5.1 ALL ENROLLED SET

The All Enrolled (ENR) set will contain all subjects who signed an informed consent for this study. This analysis set will be used to summarize subject disposition.

5.2 SAFETY ANALYSIS SET

The Safety analysis set will include all subjects who received at least one dose of Vodobatinib.

5.3 PHARMACOKINETIC ANALYSIS SET

The Pharmacokinetic Analysis Set (PAS) will include all subjects in the safety analysis set who provide at least one evaluable PK concentration with no important protocol deviations, violations or events thought to significantly affect the PK of the drug.

5.4 EFFICACY ANALYSIS SET

The Efficacy analysis set will include all subjects who received at least 1 dose of Vodobatinib.

5.5 PROTOCOL DEVIATIONS

Protocol deviations will be documented separately in a stand-alone document before database lock which include deviation category (e.g., violation of inclusion and exclusion criteria at screening, use of excluded concomitant medications, received the incorrect dose), deviation description, severity (minor/major), visit/time point for each deviation. Major protocol deviations are defined as those deviations from the protocol that threaten the integrity of the data, adversely affect subjects and/or could influence/affect the outcome of the efficacy endpoints (or part of it).

6 GENERAL ASPECTS FOR STATISTICAL ANALYSIS

6.1 GENERAL CONSIDERATIONS

Continuous data will be summarized [REDACTED]. Categorical variables will be summarized [REDACTED].

For all percentage calculations, the denominator will be the number of subjects in the analysis set, unless otherwise stated. Time-to-event data will be summarized [REDACTED].

[REDACTED]

[REDACTED]

[REDACTED]

[REDACTED]

[REDACTED]

[REDACTED]

[REDACTED]

[REDACTED]

[REDACTED]

[REDACTED]

[REDACTED]

[REDACTED]

[REDACTED]

[REDACTED]

[REDACTED]

[REDACTED]

[REDACTED]

[REDACTED]

[REDACTED]

[REDACTED]

[REDACTED]

[REDACTED]

[REDACTED]

[REDACTED]

[REDACTED]

[REDACTED]

[REDACTED]

[REDACTED]

[REDACTED]

[REDACTED]

[REDACTED]

7 DISPOSITION AND ANALYSIS SETS

The subject disposition table will be based on all enrolled subjects who are consented to participate in the study. The following summaries will be included in the disposition table: total number of subjects screened in the study, number of subjects who failed screening, number of subjects received treatment, number of subjects who discontinued treatment with reason for treatment discontinuation, number of subjects on the treatment, number of subjects under survival follow-up or have completed survival follow-up. In addition, the number of subjects included in each of the analysis sets will be presented. [REDACTED]

[REDACTED] A by-subject listing of disposition will be provided for the ENR set. The data may be further presented by dosing groups, disease types or other subgroups of interest.

8 DEMOGRAPHIC AND OTHER BASELINE CHARACTERISTICS

The safety analysis set will be used to summarize the subjects' demographics and baseline characteristics. Continuous variables (e.g., age and weight) will be summarized [REDACTED]

[REDACTED] Qualitative variables (e.g., sex, race, and ethnicity) will be summarized [REDACTED].

The demographic parameters will include age category (<65 and ≥65 years), gender, race, ethnicity. Age will also be summarized as a continuous variable. The baseline parameters include, ECOG performance status, weight, height, body mass index, ECOG performance status, baseline cardiovascular and metabolic co-morbidities. Also included will be baseline TKI status (Refractory, intolerant and resistant), history of bone marrow transplantation, baseline Ph+ cells, number of prior TKIs received, prior ponatinib treatment, prior ponatinib and asciminib treatment, baseline mutation status, extramedullary involvement (Yes/No) and baseline cytogenetic (i.e: complete or partial) and molecular responses (by BCR::ABL1 transcript %). Additionally, data will be separately presented by disease type and dosing cohorts.

By-subject listings of demographic and other baseline characteristics will be provided for safety analysis set.

9 MEDICAL AND SURGICAL HISTORY

Medical history and ongoing conditions, including cancer-related conditions and symptoms entered on eCRF will be summarized by system organ class (SOC) and preferred term (PT) overall and by dose group using safety analysis set. Subjects with more than one of the same PTs within

an SOC will be counted only once. Medical histories will be coded using a central coding dictionary, the Medical Dictionary for Regulatory Activities (MedDRA) terminology.

10 MEDICATIONS

Prior, concomitant, and post-therapies will be coded using the latest available version of the Anatomical Therapeutic Chemical (ATC) classification text from the World Health Organization Drug Dictionary (WHO DD) and summarized using safety analysis set. Surgical and medical procedures will be coded by primary system organ class (SOC) and preferred term (PT) according to MedDRA coding dictionary.

Prior therapy:

Prior therapies are therapies which started and stopped before the first dose of Vodobatinib. Any changes to prior medications (dose, regimen, etc.) during the study will be considered a new concomitant medication.

The number and percentage of subjects who received any prior including anti-neoplastic medications will be summarized by the dose group for the safety analysis set. The number and percentage of subjects who received any prior including anti-leukemic medications will be summarized by the dose group for the safety analysis set. The prior medications will be summarized for the lowest anatomical therapeutic classification (ATC) class and preferred name.

Concomitant therapies:

Concomitant therapies are defined as all interventions (medications and procedures) other than the study treatment administered to a subject coinciding with the study treatment period. Concomitant therapies include medications and medical procedures starting on or after the first dose of study treatment or starting prior to the first dose of study treatment and continuing after the first dose of study treatment. Concomitant medication will be summarized by the lowest ATC class and preferred name using frequency counts and percentages. Surgical and medical procedures will be summarized by SOC and PT. A listing will also be provided.

[REDACTED]

[REDACTED]

[REDACTED]

[REDACTED]

Hematological Response:

Hematological response is a normalization of the blood counts, particularly WBC counts and is evaluated by peripheral blood assessments and clinical assessments of extramedullary disease.

[REDACTED]

[REDACTED]

[REDACTED]

[REDACTED]

[REDACTED]

[REDACTED]

[REDACTED]

[REDACTED]

[REDACTED]

[REDACTED]

Cytogenetic Response:

Cytogenetic response is assessed by the ratio of number of Ph+ cells seen to the number of cells analyzed on Karyotyping done by the central laboratory. In cases where karyotyping was not performed then the central laboratory florescence in situ hybridization (FISH) results will be

used. When central laboratory data is not available, then data from the local laboratory will be used for the analysis. [REDACTED]

[REDACTED]

Molecular Response:

Molecular response is assessed using quantitative PCR (qPCR) based on the amount of BCR-ABL protein in the blood and is presented below in Table 2.

[REDACTED]

[REDACTED]

[REDACTED]

[REDACTED]

[REDACTED]

Cytogenetic, molecular, and hematologic responses will be summarized [REDACTED]

[REDACTED]

[REDACTED]

[REDACTED]

Criteria for Molecular Responses

[REDACTED]

Cytogenetic, molecular, and hematologic responses will be summarized [REDACTED]

[REDACTED]

Cytogenetic, molecular and hematological responses [REDACTED] will be presented [REDACTED]. The response rate at a specific time point is defined as the number of subjects who achieved the response at that time point divided by the total number of subjects in the treatment group. [REDACTED]

[REDACTED] The hematological

response will be summarized only for subjects with CML-AP and BP.

A separate summary will be provided for the best cytogenetic and molecular responses by achieved and maintained responses during the study period. The assessment for the achieved response includes all subjects who entered the study without the specific response. The assessment for the maintained response includes subjects who entered the study with the specific response.

By-subject listings of pharmacodynamic parameters will be provided for the safety analysis set. A by-subject listings will be provided for subjects who had disease progression.

Time to CCyR/MMR (in weeks), defined as the date of first documented CCyR/MMR - date of randomization + 1 divided by 7 will be summarized descriptively using number of subjects, mean, SD, median, minimum, maximum and quartiles.

Duration of CCyR/MMR, defined as the time between the date of the first documented MMR to the earliest date of confirmed loss of MMR or progression to accelerated phase (AP)/BP, or CML-related death will be summarized descriptively. The duration of CCyR/MMR (in weeks) is calculated as (end date or censoring date of CCyR/MMR - date of first CCyR/MMR + 1)/7.

All analysis will be conducted separately for all CML subjects and CML-CP subjects.

Further analyses for efficacy may be performed by dose group, stage of CML, resistance or intolerance, and mutational status.

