In Part B, Dose proportionality [REDACTED] will be assessed [REDACTED] for Cycle 1 and Cycle 2. Dose proportionality may also be [REDACTED] evaluated using the [REDACTED], if sufficient data is available (at least n=3) for a given cohort. Steady-state [REDACTED] will be evaluated [REDACTED]. Any additional pharmacokinetic evaluations will be described in the Statistical Analysis Plan (SAP).

In Part C, concentrations from the population PK will be evaluated. The details will be explained in the SAP.

Efficacy Parameters:

In Parts B : Hematological response, Cytogenetic response and Molecular response rates will be assessed for efficacy according to criteria mentioned in Appendix I (Section 13.1). All subjects will be followed for up to approximately 60 months after the first dose of K0706. Efficacy analysis will include all subjects in the efficacy analysis set.

For Part C: Hematological response, Cytogenetic response and Molecular response rates will be assessed for efficacy according to criteria mentioned in Appendix I (Section 13.1). All subjects will be followed for up to approximately 60 months after the first dose of K0706.

All efficacy analysis will be performed separately per Cohort (designated from Cohort A to C), and will include all subjects in the efficacy analysis set (Section Efficacy analysis set 6.8.3.2). Primary and secondary efficacy response rates will be summarized by both point estimates and estimation of [REDACTED] confidence intervals. Continuous PD endpoints will be summarized using descriptive statistics [REDACTED], and time-to-event endpoints will be summarized using [REDACTED] and using [REDACTED]. Detailed information for censoring rules for PFS and OS will be incorporated in the SAP. More detailed information about estimation of treatment effects, summarization of data, graphical representations, and analysis conventions will be provided in the SAP. PD evaluations if undertaken will be described in the Statistical Analysis Plan.

Safety Parameters:

In general, descriptive summaries will be presented for the safety variables collected. Continuous variables will be summarized using mean, standard deviation, minimum, median, and maximum.

Categorical variables will be summarized using frequency counts and percentages. For time-to-event variables other percentiles will be presented.

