7.2.2 Secondary Objectives

To evaluate

- Anti-leukemic efficacy of K0706 by molecular outcomes
- Anti-leukemic efficacy of K0706 by hematological outcomes in CML-CP
- Anti-leukemic efficacy of K0706 by cytogenetic outcomes in CML-AP and BP
- Time to first hematologic response
- Duration of response
- Progression free survival (PFS) and Overall survival (OS).
- Population PK of K0706.
- Safety of K0706 in the dosed subjects.

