7.3.1.4.2 Secondary Endpoints

- In subjects with CML-CP, the objectives will be to evaluate the:
 - Hematological responses: Proportion of subjects who achieve or maintain complete hematological response
 - Cytogenetic response: Proportion of subjects who achieve CCyR
 - Molecular responses: Proportion of subjects who achieve major molecular response (MMR)
- In subjects with CML-AP, or CML-BP, the objectives will be to evaluate the:
 - Cytogenetic responses: Proportion of subjects who achieve CCyR, PCyR,
 - Molecular responses: Proportion of subjects who achieve MMR

- In all subjects: Safety and tolerability in terms of incidence and severity of treatment emergent AEs
- In all subjects: Time to response, duration of response, PFS and OS

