7.8.1 Primary and Secondary Target Variables

Primary Endpoints

- Cohort A: For CML subjects in CP at study entry: major cytogenetic response (MCyR), defined as complete cytogenetic response (CCyR) or partial cytogenetic response (PCyR). (CP subjects in CCyR are not eligible for this study)
For subjects entering the study in PCyR, achieving CCyR on the study drug will be considered as MCyR.
- Cohort B: For CML subjects in AP at study entry: major hematologic response (MaHR), defined as complete hematologic response (CHR) or no evidence of leukemia (NEL). (AP subjects in MaHR are not eligible for this study)
- Cohort C : For CML subjects in BP : MaHR, consisting of CHR
Or NEL. (BP subjects in MaHR are not eligible for this study)

Secondary Endpoints

- In subjects with CML-CP
 - Hematological responses: Proportion of subjects who develop complete hematological response
 - Cytogenetic responses: Proportion of subjects who develop CCyR
 - Molecular responses: Proportion of subjects who achieve MMR
- In subjects with CML-AP or CML-BP

- Cytogenetic responses: Proportion of subjects who achieve CCyR or PCyR,
- Molecular responses: Proportion of subjects who achieve MMR
- In all subjects: Safety and tolerability in terms of incidence and severity of treatment emergent AEs
- In all subjects: Time to response, duration of response, progression free survival and overall survival

Table 7-13 Efficacy Assessment of Primary End points

| | Cohort A | | Cohort B and C ^a |
|-------------------------------|---|--|---|
| Primary endpoint will include | Subjects entering the study with less than PCyR | Unconfirmed MCyR: That is detection of a complete or partial cytogenetic response on a single bone marrow aspirate will qualify as a response for determination of efficacy. | Confirmed MaHR: This includes demonstration of CHR or NEL confirmed by 2 hematological assessments performed at least 4 weeks apart. The hematological assessments will include a peripheral blood CBC and differential to qualify as a response. |
| | Subjects entering the study with PCyR | Unconfirmed CCyR: That is detection of Complete cytogenetic response on a single bone marrow aspirate will qualify as a response for determination of efficacy. | |

a: Criteria for responses are included in Appendix 1

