13 APPENDIX

13.1 APPENDIX I

CRITERIA FOR RESPONSE

Haematological response

Major haematological response (MaHR) is inclusive of complete haematological response (CHR) and/or no evidence of leukemia (NEL).

For subjects who enter the study in MaHR response, the criteria for evaluating response is: Maintenance of MaHR for upto 12 weeks after initiation of study treatment.

These criteria are adapted from Talpaz et al., 2006, O'Brien et al., 2003, and Kantarjian et al., 2010.

| Haematological response criteria for Subjects with CML-AP and CML-BP and Ph+ ALL | |
|--|---|
| CHR | 
 • White blood cells (WBCs) \leq Institutional upper limit of normal • $ANC \geq 1000/mm^3$ • Platelets $\geq 100,000/m^3$ • No blasts or promyelocytes in peripheral blood • $< 5\%$ basophils on differential • $< 5\%$ myelocytes and metamyelocytes on peripheral blood • No extra-medullary involvement (no hepatomegaly and/or splenomegaly) |
| NEL | 
White blood cells (WBCs) \leq Institutional upper limit of normal
 
No blasts or promyelocytes in peripheral blood
 
$< 5\%$ basophils on differential
 
$< 5\%$ myelocytes and metamyelocytes on peripheral blood
 
No extra-medullary involvement (no hepatomegaly and/or splenomegaly)
 
At least one of the following
 
 • $20,000/mm^3 \leq Platelets \leq 100,000/mm^3$ • $500/mm^3 \leq ANC \leq 1000/mm^3$ |

| Complete haematological response (CHR) for Subjects with CML-CP | |
|---|--|
| CHR | 
Platelets $< 450 \times 10^9/mm^3$
 
White blood cells (WBCs) \leq Institutional upper limit of normal
 
No blasts or promyelocytes in peripheral blood
 
$< 5\%$ basophils on differential
 |

| | |
|--|---|
| | < 5 % myelocytes and metamyelocytes on peripheral blood No extra-medullary involvement (no hepatomegaly and/or splenomegaly) |
|--|---|

Cytogenetic response:

Criteria for Cytogenetic response have been derived from Kantarjian et al, 2006, Talpaz et al, 2006 and National Comprehensive Cancer Network (NCCN), Clinical practice guidelines (2018).

At least 20 metaphase should be evaluated. If fewer metaphases are reported, absolute percentage values should be reported. Peripheral blood cells must not be used.

| Major Response | Cytogenetic Response | Complete (CCyR) | No Ph+ Cells |
|------------------|----------------------|-------------------------|--------------------|
| | | Partial Response (PCyR) | 1-35 % Ph+ Cells |

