2.2 PART C

Primary Objective

- To evaluate the anti-leukemic efficacy of Vodobatinib in subjects with CML-CP by cytogenetic outcomes and in subjects with CML-AP and BP by hematologic outcomes who have failed ≥ 3 TKIs, one of which includes ponatinib.

Secondary Objectives

- Anti-leukemic efficacy of Vodobatinib by molecular outcomes.
- Anti-leukemic efficacy of Vodobatinib by hematological outcomes in CML-CP.
- Anti-leukemic efficacy of Vodobatinib by cytogenetic outcomes in CML-AP and BP.
- Time to response.
- Duration of response.
- Progression free survival (PFS) and Overall survival (OS).
- Population PK of Vodobatinib.
- Safety of Vodobatinib.

Exploratory Objectives

- To evaluate the correlation of therapeutic activity of Vodobatinib in the context of different baseline BCR-ABL mutation profiles.
- To evaluate the BCR-ABL mutation profile at disease progression (should it occur) for possible mechanisms of resistance.

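### The SAP text as printed limits the hematologic response summary to CML-AP and BP, so complete hematologic response in CML-CP, a Part C secondary endpoint, has no readable planned estimate, and the protocol words that endpoint two ways

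*SAP*

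**What the plan says.** **Protocol.** Section 7.2.2 lists as a secondary objective "Anti-leukemic efficacy of K0706 by hematological outcomes in CML-CP". For subjects with CML-CP, Section 7.3.1.4.2 defines the matching endpoint as "Hematological responses: Proportion of subjects who achieve or maintain complete hematological response", and the Protocol Summary uses the same words. Section 7.8.1, in the statistical methods, has instead "Hematological responses: Proportion of subjects who develop complete hematological response". Appendix I (Section 13.1) has a separate table headed "Complete haematological response (CHR) for Subjects with CML-CP". On reporting, the Protocol Summary states that "Primary and secondary efficacy response rates will be summarized by both point estimates and estimation of" confidence intervals, with the level blacked out. Section 7.8.5 repeats this.

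**SAP.** Section 2.2 keeps the secondary objective: "Anti-leukemic efficacy of Vodobatinib by hematological outcomes in CML-CP". The efficacy text has its heading redacted and lies between Section 10 (Medications) and Section 13 (Survival). It says that the hematological "response will be summarized only for subjects with CML-AP and BP". It then adds: "A separate summary will be provided for the best cytogenetic and molecular responses by achieved and maintained responses during the study period". Hematologic response is not named there. A few lines later the same text says that all analysis is to be run separately for all CML subjects and for CML-CP subjects.

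**The concern.** The SAP keeps an objective and, in the text that should deliver it, prints a sentence that leaves out the only population to which the objective applies. A programmer who follows that sentence produces no CHR estimate for Cohort A. A programmer who follows the later sentence about separate CML-CP analyses produces one. The two instructions cannot both be carried out.

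The second difficulty appears once the summary is restored. The protocol does not say with one voice what is to be counted. One wording credits subjects who arrive in CHR and stay there; the other appears to credit only those who newly reach it. At stake is whether a pre-specified secondary endpoint of what the protocol calls its pivotal part is estimated at all and, if so, which proportion carries its name.

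**Working it through.** **Step 1: is there a planned CHR estimate for CP?** The documents state no figure to reproduce, so this is a comparison of text.

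| Place | Hematologic response in CML-CP |
|---|---|
| Protocol 7.2.2; SAP 2.2 | Secondary objective |
| Protocol Summary; 7.3.1.4.2 | Secondary endpoint, achieved or maintained CHR |
| Protocol 7.8.1 | Secondary endpoint, developed CHR |
| Protocol Appendix I | CP-specific CHR criteria given |
| Protocol Summary; 7.8.5 | Secondary response rates get a point estimate and interval |
| SAP efficacy text, restriction sentence | Not summarized (AP and BP only) |
| SAP efficacy text, achieved and maintained summary | Cytogenetic and molecular only |
| SAP efficacy text, later sentence | All analysis also run for CML-CP |

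The readable SAP contains one sentence against a CP summary, one general sentence in favour, and none that specifies it.

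**Step 2: can CP subjects enter in CHR?** The endpoint text in Protocol 7.3.1.4.1 bars CP subjects in complete cytogenetic response and AP or BP subjects in major hematologic response. It states no bar for CP subjects in CHR. Inclusion criterion 3 (7.3.2.1.1) admits CP subjects who meet any one resistance criterion, which may be cytogenetic or molecular only, or who are intolerant. The word *maintain* would have no content if nobody could enter in CHR. So the two wordings can give different numbers.

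**Step 3: how far apart are they?** The documents give none of the inputs, so all three are assumptions:

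- h = share of dosed Cohort A subjects in CHR at entry, varied from 30% to 90%
- k = share of those who keep it, 85%
- g = share of the rest who gain it, 50%

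The denominator is all dosed subjects, following the efficacy analysis set (Protocol 7.8.3.2; SAP 5.4).

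- Achieve or maintain = h × k + (1 − h) × g
- Develop = (1 − h) × g
- Gap = h × k

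| h | Achieve or maintain | Develop | Gap |
|---|---|---|---|
| 30% | 0.30 × 0.85 + 0.70 × 0.50 = 60.5% | 0.70 × 0.50 = 35% | 25.5 points |
| 70% | 0.70 × 0.85 + 0.30 × 0.50 = 74.5% | 0.30 × 0.50 = 15% | 59.5 points |
| 90% | 0.90 × 0.85 + 0.10 × 0.50 = 81.5% | 0.10 × 0.50 = 5% | 76.5 points |

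As entry prevalence rises, one figure goes up and the other goes down. The gap is exactly the maintained component, so it vanishes only if no subject both enters in CHR and keeps it.

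**The case against.** The best defence is the redaction. The restriction sentence follows blacked-out text, at the end of a paragraph about response at a specific time point, and may govern only that display. Twice earlier in the same section the SAP says hematologic responses will be summarized, with the rest of the sentence blacked out and no readable limit by phase. The hematologic criteria are also redacted, and the readable text does not show whether the sentence is for Part B, Part C or both. This stands. A reader might infer that CP is shut out of every hematologic summary or that the endpoint has been deleted. The documents do not establish that: the objective remains in SAP 2.2, by-subject listings are planned, and the sentence about separate CML-CP analyses points the other way. What remains is that the sentence is complete and unqualified as printed. If a narrower scope was meant, it still has to be written down.

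A reader might also infer that PFS is compromised, because loss of CHR counts as progression in CP (Protocol Table 7-3). That does not follow. Progression is identified subject by subject from blood counts, and SAP Section 13 defines PFS from documented progression requiring withdrawal, or death. Leaving out a table of CHR rates changes neither.

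Nor do the documents show that the definition would be picked after seeing results. Both dedicated endpoint lists already say *achieve or maintain*, and only Section 7.8.1 differs. Finally, the endpoint is descriptive: Protocol 7.8 plans no formal testing of treatment effects, and the blood counts are collected, so the rate can be recovered.

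**Conclusion.** The inconsistency is real and should be fixed. As printed, the SAP's restriction to AP and BP contradicts the protocol's CHR endpoint in CML-CP, the SAP's own objective and a later sentence in the same SAP section. No readable text provides the estimate. Redacted text could narrow the restriction, so confidence is high that the printed sentences conflict and only moderate about how many displays are affected.

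The two protocol wordings name different proportions. Under the assumed 85% kept and 50% gained, they differ by 25.5 to 76.5 percentage points as CHR at entry runs from 30% to 90%. Those inputs are illustrative. The direction does not depend on them, provided some CP subjects enter in CHR and keep it.

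The consequence is limited to one secondary, descriptive endpoint. Major cytogenetic response, the primary endpoint of Cohort A, does not depend on it, and neither does the PFS definition. The documents do not support calling Cohort A the main cohort: cohort sizes are redacted, and Protocol 7.3.1 treats the cohorts as separate studies.

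**What to change.** 1. **SAP efficacy text.** Remove the restriction to AP and BP, or name the one display to which it applies. Make it consistent with the sentence on separate CML-CP analyses.
2. **SAP, new table.** Suggested wording: *For Cohort A, CHR by the Appendix I criteria for CML-CP will be summarized as the proportion of all dosed subjects who achieve or maintain CHR, with point estimate and confidence interval. The achieved component (subjects without CHR at baseline) and the maintained component (subjects with CHR at baseline) will be shown separately.* This extends to CHR the split the SAP already plans for cytogenetic and molecular response.
3. **Protocol 7.8.1.** Align *develop* with the *achieve or maintain* wording of the Protocol Summary and Section 7.3.1.4.2.
4. **Maintained.** Appendix I says that subjects entering in major hematologic response, which includes CHR, are judged on keeping it for up to 12 weeks. State whether this governs maintained CHR in CP. Unless the redacted criteria already do so, also state whether a single assessment suffices, since Table 7-13 covers primary endpoints only.

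If the sponsor did intend to drop CHR in CP, the alternative is to remove it from the protocol and SAP with a stated reason.

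The cost is a few sentences in the SAP, a wording change in the protocol and one additional table. No new data are needed, because the blood counts are already collected.

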6.4.8 Randomization Procedures

Subjects in the study will not be randomized. All eligible subjects will be assigned to treatment with K0706. Subjects will be sequentially assigned to a specific cohort as they are enrolled in the study.

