7.4.8 Randomization Procedures

All eligible subjects will be assigned to treatment with K0706. Enrollment into the assigned cohorts will be parallel.

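### The SAP starts time to response at a randomization date that does not exist, and defines CCyR duration by MMR dates that conflict with its own formula

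*SAP*

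**What the plan says.** The rules stand in the SAP's efficacy text between Sections 10 and 13, where the section heading is redacted.

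- **Time to response.** It is computed in weeks as "date of first documented CCyR/MMR - date of randomization + 1 divided by 7" and summarised by mean, SD, median, range and quartiles.
- **Duration, in prose.** "Duration of CCyR/MMR, defined as the time between the date of the first documented MMR to the earliest date of confirmed loss of MMR". The other end events are "progression to accelerated phase (AP)/BP, or CML-related death will be summarized descriptively".
- **Duration, as a formula.** After an opening parenthesis, the next sentence gives "end date or censoring date of CCyR/MMR - date of first CCyR/MMR + 1)/7".

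On the design, Protocol 6.4.8 says of Part B that "Subjects in the study will not be randomized". Protocol 7.4.8 says of Part C that "All eligible subjects will be assigned to treatment with K0706", and SAP 3.2 calls Part C single arm. SAP Section 13 starts both OS and PFS at first dose and counts deaths of any cause in both.

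Protocol 7.3.1.4.2 lists time to response and duration of response as secondary endpoints for all Part C subjects. Protocol 7.2.2 words one of the objectives as "Time to first hematologic response".

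**The concern.** Part C has no control arm and the protocol calls it pivotal, so how quickly responses appear and how long they last are a large part of the supporting evidence. A programmer working from this text would have to invent the origin for one endpoint and choose between two start dates for the other. The event that should end a CCyR, namely its loss, is not in the list. Two programmers could each follow the SAP and report different CCyR durations from the same data.

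Three further matters in the same sentences are left open: when a continuing response is censored, what happens when a responder dies of something other than CML, and which estimator is used for duration.

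**Working it through.** The documents state no numerical result or assumption for these endpoints, so there is no figure to reproduce. The check is a comparison of the text, followed by a labelled illustration.

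**1. Origin of time to response.** The formula needs a randomization date. Part B has none by Protocol 6.4.8, and Part C has none because it is a single-arm study. The survival endpoints in SAP Section 13 use first dose, which every member of the SAP's efficacy set has by definition (SAP 5.4).

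**2. Missing parentheses.** Put first dose on day 1 and response on day 85. With parentheses: (85 − 1 + 1)/7 = 12.14 weeks. Read literally without them: 85 − 1 + 1/7 = 84.14, which is not in weeks. The duration formula has its parentheses; the time-to-response formula does not.

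**3. Duration of CCyR.** For one subject let C1 and CL be the dates of first CCyR and its confirmed loss, and M1 and ML the same for MMR. Ignoring the one added day:

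- Prose definition: ML − M1.
- Formula, with the loss event named in the prose: ML − C1.
- A duration that belongs to CCyR: CL − C1.

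The first two differ by M1 − C1. If MMR comes after CCyR and is lost before it (an assumption), the prose falls short of CL − C1 by (M1 − C1) + (CL − ML), and the formula by CL − ML. For a subject who reaches CCyR but never MMR, the prose gives no value. The formula does have a start for that subject, but losing CCyR does not end the response, so it runs on to phase progression, CML death or censoring. The error can therefore go in either direction.

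**4. Other end events.** The SAP ends a response at progression to AP or BP. Protocol Table 7-3 (Part C) and Table 6-2 (Part B) are wider and specific to phase. In chronic phase, for example, loss of MCyR or a sustained rise in white cells or platelets also counts. A subject already in blast phase cannot newly progress to AP or BP, so that event does not serve Cohort C. Both tables list death without limiting it to CML, as PFS does.

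**5. Illustration only: every input is assumed.** Suppose event times and censoring times were pooled and summarised as if all were complete. Take exponential durations with true median m weeks, so λ = ln 2/m, and follow-up after response uniform on 0 to F weeks. The reported median t solves exp(−λt)(1 − t/F) = 0.5, and the censored share is (1 − exp(−λF))/(λF).

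| F (weeks) | True median | Reported median | Censored |
|---|---|---|---|
| 130 | 52 | 31.3 | 48% |
| 130 | 104 | 43.3 | 67% |
| 130 | 208 | 52.6 | 81% |
| 260 | 52 | 39.6 | 28% |
| 260 | 104 | 62.6 | 48% |
| 260 | 208 | 86.5 | 67% |

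The fall runs from (52 − 39.6)/52 = 24% to (208 − 52.6)/208 = 75%.

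Suppose instead that a proper censored-data method were used and non-CML deaths, a share s of all end events, were censored. With constant hazards the median becomes m/(1 − s). For m = 104 and s = 10% that is 104/0.9 = 115.6 weeks; for s = 20% it is 104/0.8 = 130 weeks.

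**The case against.** The best defence is that these are drafting slips with an obvious intention. Randomization is leftover wording that also appears in Protocol 6.5.3.1, 6.7.2 and 7.5.3.1, and first dose is the evident substitute. The duration formula does start at CCyR. The endpoints are secondary, with no formal testing (Protocol 7.8). That limits the consequence, but it does not make the text correct: an SAP is followed as written, and the formula supplies only the start for CCyR, not its end event.

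A reader might infer more, and the documents do not support it:

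- **That CCyR duration will be timed from MMR.** The prose says so and the formula does not. The defect is the conflict between them, together with the missing loss event.
- **That continuing responses will be summarised as if they had ended.** A descriptive summary of a quantity that accepts a censoring date permits this reading. However, the list of mean and median belongs to the time-to-response sentence, and the general time-to-event methods (SAP 6.1, Protocol 7.8 and the protocol summary) are stated but redacted. Kaplan-Meier may be specified there.
- **That deaths not due to CML are ignored.** They are not end events, but the text does not say whether they are censored or treated as a competing risk. Counting only CML-related death may be a deliberate choice; it is unexplained and differs from PFS.
- **That duration is biased downward by censoring and upward by excluded deaths at once.** If censoring times are pooled as complete, a response censored at a non-CML death is already treated as ended there. The upward bias needs proper censored-data estimation, and the downward bias arises only without it.
- **That MCyR and MaHR have no such rules.** None is visible, but substantial parts of the efficacy text are redacted, so absence cannot be shown.

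**Conclusion.** The SAP is wrong as written on two points, both in unredacted text. Time to CCyR/MMR has an origin that exists in neither Part B nor Part C. The definition of CCyR duration uses MMR dates, conflicts with its own formula on the start date, and never names loss of CCyR as an end event. Neither conclusion rests on an assumption.

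No size can be given from the documents. The figures above show what a naive summary, or censoring of non-CML deaths, would do under assumed inputs, and are not estimates for this trial. The direction of the first is general: whenever responses continue at cut-off, pooling censoring dates with end dates pulls the median down. Whether the plan does this is not established.

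The consequence is confined to secondary endpoints. The primary MCyR and MaHR rates do not depend on these definitions.

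**What to change.** Revise the SAP's efficacy text before programming:

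1. Time to response = (date of first response − date of first dose + 1)/7, with the parentheses.
2. Define the two durations separately: CCyR from first CCyR to confirmed loss of CCyR, and MMR from first MMR to confirmed loss of MMR. Each also ends at progression under the protocol's phase-specific criteria (Table 6-2 for Part B, Table 7-3 for Part C) or at death.
3. State the censoring date for duration.
4. Either count death from any cause, as PFS does, or justify counting CML-related death only and say whether other deaths are censored or a competing risk.
5. Unless the redacted time-to-event text already covers duration, name Kaplan-Meier as the estimator, or cumulative incidence if other deaths are competing risks.
6. Confirm that the redacted text gives matching rules for MaHR and for MCyR, where a subject entering in PCyR responds only on reaching CCyR (Protocol 7.8.1).

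The cost is SAP wording and programming, with no change to conduct or data collection. The drawback is that some medians may be reported as not reached instead of as a single number.
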